14.5 Analysis Methods

14.5.1 Timing of Analysis

The primary analysis will occur after VGPR+ status (yes or no) has been determined for all subjects. Secondary endpoints will also be assessed at the time of the primary analyses. Updated analyses will be conducted after the PFS censoring rate reaches 20% or when all surviving subjects who are not lost to follow up or have not been withdrawn from the study have been on study for at least 3 years, whichever occurs first. A final analysis will be conducted after the overall survival censoring rate reaches 20% or after all surviving subjects who are not lost to follow up or have not been withdrawn from the study have been on study for at least 5 years, whichever occurs first.

14.5.2 Subject Disposition

A disposition summary of all consenting subjects will be provided. This will include a summary of subjects who consented, were treated, discontinued treatment, died, and were lost to follow-up or withdrew consent.

14.5.3 Baseline Subject and Disease Characteristics

A summary of subject demographics and disease-related characteristics will be summarized and evaluated. These results will be qualitatively compared to patient and disease characteristics in the same patient population that have been previously reported.

14.5.4 Primary Analysis

The frequency and proportion of subjects experiencing a VGPR+ will be calculated. A corresponding 95% confidence interval will be estimated using the Clopper-Pearson method. A one-sided test for binomial proportions using the rejection region described in the sample size section (Section 14.2) will be carried out, testing the null hypothesis that the VGPR+ rate is less than or equal to 40%. Based on the design and corresponding sample size calculations described in Section 14.2, if at least 21 subjects experience a VGPR+, the null hypothesis can be rejected.

Logistic regression techniques will be used to correlate VGRR+ rate with baseline subject and disease characteristics, and results from biomarker studies as previously described. This will include univariate and multivariable regression model techniques to identify individual and independent prognostic factors.

14.5.5 Secondary Analysis

The frequencies and proportions of overall response will be calculated. Corresponding 95% confidence intervals will be estimated using the Clopper-Pearson method. OS, PFS, TTP, TTNT, and DoR endpoints will be analyzed using Kaplan Meier techniques. Selected landmarks will be estimated and reported. Logistic regression models and Cox proportional hazards models will be used to analyze the treatment response endpoints as functions of baseline subject and disease characteristics, and results from biomarker studies as previously described. The percent of subjects achieving MRD negative status will be summarized. Subgroup analyses will be conducted for selected efficacy endpoints on the subset of MRD negative subjects (i.e. time to event endpoints).

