
For MRD assessment, the first bone marrow aspirate should be sent to MRD (not for morphology) and this sample should be taken in one draw with a volume of minimally 2 mL (to obtain sufficient cells), but maximally 4–5 mL to avoid hemodilution.
 
*All response categories require two consecutive assessments made at any time before the institution of any new therapy; for MRD there is no need for two consecutive assessments, but information on MRD after each treatment stage is recommended (e.g. after induction, high-dose therapy/ASCT, consolidation, maintenance). MRD tests should be initiated only at the time of suspected complete response. All categories of response and MRD require no known evidence of progressive or new bone lesions or extra medullary plasmacytomas if radiographic studies were performed. However, radiographic studies are not required to satisfy these response requirements except for the requirement of FDG PET if imaging MRD-negative status is reported.
 
†Sustained MRD negativity when reported should also annotate the method used (e.g. sustained flow MRD-negative, sustained sequencing MRD-negative).
	

‡ Bone marrow MFC should follow NGF guidelines²⁶. The reference NGF method is an eight-colour two-tube approach, which has been extensively validated. The two-tube approach improves reliability, consistency, and sensitivity because of the acquisition of a greater number of cells. The eight-colour technology is widely available globally and the NGF method has already been adopted in many flow laboratories worldwide. The complete eight-colour method is most efficient using a lyophilised mixture of antibodies which reduces errors, time, and costs. 5 million cells should be assessed. The FCM method employed should have a sensitivity of detection of at least 1 in 10⁵ plasma cells.

§ DNA sequencing assay on bone marrow aspirate should use a validated assay such as LymphoSIGHT (Sequentia).

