14.3.3 Overall Survival

Overall survival (OS) is defined as the duration from enrollment to the study (treatment start date) to the date of death from any cause. Subjects who are alive or lost to follow-up at the time of the analysis will be censored at the last known date they were alive.

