14.3.4 Progression Free Survival

Progression free survival (PFS) is defined as the duration of time from enrollment to the study (treatment start date) to first occurrence of either PD or death. Disease progression must be objectively determined per IMWG 2016 criteria (see Section 13.1), where the date of progression is the date of the last assessment that identified PD. If the subject died without documented disease progression, the date of progression will be the date of death. For surviving subjects who do not have documented disease progression, PFS will be censored at the date of last disease assessment. For subjects who receive subsequent anti-cancer therapy prior to documented disease progression, PFS will be censored at the date of last disease assessment prior to the commencement of subsequent therapy. Subjects who have an initial PFS event immediately following 2 or more consecutive missed disease assessments will be censored at the date of the last assessment prior to those missed assessments. For participants with only one missed assessment, the documented PD status and assessment date will be used.

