14.4 Analysis Populations

Analyses of response endpoints (response evaluable population) will be conducted on the population of subjects who initiate treatment with elotuzumab and who have measurable disease at baseline. Analyses of other efficacy and safety endpoints will be conducted on the population of subjects who initiate treatment with elotuzumab. Exploratory analyses will be conducted on the population of subjects who initiate treatment with elotuzumab treatment and who have available biomarker data.

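### Time-to-event curves for the MRD-negative subset, counted from treatment start, include event-free time that is guaranteed by how the subset is defined

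*Combined protocol and SAP*

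**What the plan says.** Section 14.5.5 (Secondary Analysis) contains two MRD analyses. One is a rate: "The percent of subjects achieving MRD negative status will be summarized". The other is a set of time-to-event analyses: "Subgroup analyses will be conducted for selected efficacy endpoints on the subset of MRD negative subjects (i.e. time to event endpoints". Neither has a stated MRD time point.

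**Time origins.** Section 14.3.4 defines PFS as "the duration of time from enrollment to the study (treatment start date) to first occurrence of either PD or death", and TTP (14.3.5) follows PFS. Section 14.3.3 says "Overall survival (OS) is defined as the duration from enrollment to the study (treatment start date) to the date of death". TTNT (14.3.7) also starts at treatment start. DoR (14.3.6) is the exception and starts at the first assessment showing response.

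**When MRD is known.** The table in Section 13.1 makes CR a precondition for MRD negativity. Footnote 13 of the Study Calendar schedules marrow at screening, post-induction (within 7 days before maintenance Cycle 1 Day 1) and to confirm a CR. It adds 6-monthly marrow in maintenance as standard-of-care disease evaluation. Section 5.2 starts maintenance 28 days after the start of induction cycle 4.

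**Who is tested and counted.** A footnote in 13.1 says "MRD tests should be initiated only at the time of suspected complete response". Section 1.4.1 instead plans an MRD flow assay at every marrow time point, and 8.8.3 assigns MRD testing to the calendar marrows. MRD is an exploratory objective (2.4), and Section 14.4 limits exploratory analyses to treated subjects "who have available biomarker data".

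**The concern.** Membership of the MRD-negative subset is decided after the clock has started. Anyone who progresses or dies before the qualifying marrow cannot enter it, so the subset has no events in that interval by construction. A Kaplan-Meier curve drawn from Cycle 1 Day 1 credits this interval to MRD negativity.

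The error always runs in the same direction, making MRD-negative subjects look better. A single-arm trial of 40 has no concurrent control that would expose it. The likely use of such a curve is to set it beside the whole cohort or published series, and there the guaranteed interval would read as prognosis.

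**Working it through.** The plan gives no figure for the MRD analyses, so there is none to reproduce.

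**Inputs**
- Post-induction marrow: 4 cycles × 28 days = 112 days; 112 / 30.4375 = 3.68 months (Sections 5.1, 5.2 and calendar footnote 13). Call this g.
- Median PFS M on KRd: 15.4 months in the phase II cohort and 26.3 months in the phase III trial (Section 1.2).
- Assumptions: exponential PFS, S(t) = 2^(−t/M), and MRD status unrelated to prognosis. Any gain in the subset is then pure artefact.

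**Step 1. One read at the post-induction marrow.** In the subset, PFS from treatment start is S(t)/S(g) for t > g, so the median is M + g.

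| True median | S(g) | Subset median | 12-month PFS, all | 12-month PFS, subset |
|---|---|---|---|---|
| 15.4 | 0.847 | 19.1 | 58% | 0.583/0.847 = 69% |
| 26.3 | 0.908 | 30.0 | 73% | 0.729/0.908 = 80% |

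At 36 months with M = 26.3, S = 0.387 and the subset shows 0.387/0.908 = 43%, against 39% in all subjects. The share with an event before g is 1 − S(g), or 15% and 9%. That is about 6 and 4 of 40 subjects who could never qualify.

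**Step 2. Later conversions also count.** Suppose conversions are read at g, g+6, g+12 and g+18 months, and a fraction w of potential converters is assigned to each visit. Beyond the last visit the subset median solves S(t) = ½ Σ w·S(visit). With M = 26.3, S at the four visits is 0.908, 0.775, 0.662 and 0.565.
- Weights 0.80, 0.10, 0.05, 0.05: Σ = 0.865, S(t) = 0.432, median 31.8 months.
- Equal weights of 0.25: Σ = 0.727, S(t) = 0.364, median 38.4 months.

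A simulation of 1,000,000 subjects used a different schedule: 30% negative at g, then 10% to 20% of those still event-free and not yet negative converting at each 6-monthly marrow. It gave subset medians of 40.6 to 40.9 months (true 26.3) and 25.6 to 26.8 months (true 15.4). The conversion schedules are assumptions, so these figures show direction and sensitivity only.

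**Step 3. Check on the cause.** In the same simulation, with the clock started at the MRD-negative date, the subset medians returned to 15.4 and 26.3 months within simulation error. The inflation comes from the time origin.

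**Step 4. MRD rate.** Taking 12 negatives as an assumption, the rate is 12/40 = 30%, 12/30 = 40% or 12/20 = 60%, depending on who is counted.

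**The case against.** The strongest reply is that little depends on this analysis. MRD is exploratory, the subset analysis carries no hypothesis, alpha or decision rule, and 14.5.5 states no comparison with MRD-positive subjects. A labelled descriptive curve misleads mainly when set against others. The subset will also be small: for an assumed 8 MRD-negative subjects and a true median of 26.3 months, the 95% sampling range of the observed median is about 9 to 60 months by simulation, far wider than a 3.7-month bias. This stands as a limit on importance. It does not remove the bias, which is systematic and cheap to avoid.

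Section 14.5.5 does say "Selected landmarks will be estimated and reported", and a reader might take that as the remedy. It follows directly on the Kaplan-Meier sentence and most naturally means survival estimates at fixed times, not a restarted clock for MRD.

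Three stronger readings are tempting, and the documents do not support them.
- **A large gap between MRD-negative and other subjects.** No such contrast is planned, and its size would depend on assumed conversion times. The 6-monthly marrows are described as standard-of-care evaluation, so MRD reads at those visits are not clearly planned.
- **An MRD rate calculated among responders only.** This follows from the 13.1 footnote and the exploratory population taken together. However, 1.4.1 and 8.8.3 plan MRD testing at scheduled marrows, the rate is listed under Secondary Analysis, and 14.4 analyses other efficacy endpoints in everyone who starts elotuzumab. The supportable statement is that the denominator is unstated and the sections disagree.
- **The same bias in the Cox models.** Section 14.5.5 does not say whether the biomarker covariates are baseline or later values. The issue arises only if later values enter as fixed covariates.

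**Conclusion.** The point holds for the time-to-event analyses in the MRD-negative subset. Under exponential PFS and no true MRD effect, a post-induction read adds about 3.7 months to the median (15.4 to 19.1, or 26.3 to 30.0). In the latter case it adds about 4 percentage points to 36-month PFS. If any later MRD-negative result qualifies, the inflation is larger, but its size cannot be fixed from the documents. If CR is confirmed by marrow during induction, the guaranteed interval is shorter than 3.7 months.

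PFS, TTP, OS and TTNT are affected; the figures were worked for PFS. DoR is affected less, because only the interval from first response to the MRD-negative marrow is guaranteed. The primary VGPR+ test is untouched. This is a worthwhile, inexpensive correction to a descriptive secondary analysis, not a flaw in the trial's main conclusion. The unstated denominator of the MRD rate is a matter of missing detail.

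**What to change.** In Section 14.5.5, replace the subset analysis from treatment start with one of the following:
- **Landmark analysis** at the post-induction evaluation: include subjects event-free at that date, group them by MRD status known by then, and count time from that date.
- **Time-dependent covariate:** enter MRD status in the Cox model so that it changes at the date negativity is found. This uses later conversions.

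Treat any other post-baseline biomarker in the Cox models in the same way.

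For the MRD-negative rate, state the time point and report it over all response-evaluable subjects, with untested subjects counted as not negative. Add a tested-only rate as a sensitivity analysis. Research sampling was stopped under Amendment 7 (calendar footnote 13; Section 8.8), so counting a CR subject left untested for that reason as not negative pulls the main rate down. Reconcile 1.4.1 and 8.8.3 with the testing footnote in 13.1, and say which population in 14.4 applies.

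The cost is SAP wording and minor programming, with no new data. Subjects with an event before the landmark leave this one analysis (about 4 to 6 of 40 under the medians above), and a post-induction landmark ignores later conversions.

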14.5.6 Safety Analysis

Incident rates for treatment-emergent adverse events, adverse events leading to study drug discontinuation, SAEs and deaths while on study therapy will be summarized. Treatment-emergent adverse events are defined as follows:

- An adverse event that occurs after treatment start that was not present at the time of treatment start; **OR**
- An adverse event that increases in severity after treatment start if the event was present at the time of treatment start.

Cumulative doses will be calculated for each subject (for elotuzumab, carfilzomib and lenalidomide) in both absolute terms and as a percent of expected cumulative dose (relative dose intensity). Cumulative dose and relative dose intensity will then be summarized for the study arm.

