5. STUDY PLAN

See Schema (page III).

This single arm, open-label phase II study is designed with the primary objective of evaluating the efficacy of induction therapy comprised of 4 cycles of carfilzomib, lenalidomide, dexamethasone and elotuzumab (KRd+elotuzumab) in terms of VGPR+ in subjects with relapsed or refractory multiple myeloma, and comparing to relevant historical controls. Post induction, all subjects will undergo disease evaluation for assessment of the primary endpoint. Maintenance therapy comprised of elotuzumab and lenalidomide (R+elotuzumab) will start directly after induction and continue until relapse or progression.

This study will initially open as a single center study at LCI and additional investigational site(s) may be added following activation at the coordinating center. We anticipate subjects will be accrued over 24 months.

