5.2 R+Elotuzumab Maintenance Regimen

The first cycle of maintenance therapy will begin 4 weeks (28D) after the start of cycle 4 of induction. **NOTE:** premedication (including dexamethasone) is required prior to elotuzumab as described in Section 6.4.1.

Table 2: R+Elotuzumab Maintenance Regimen

Drug	Dose	Route	Schedule	4-Week (28D) Cycle
Lenalidomide	15 mg or LTD if <15mg ^a	Oral	Once a day at bedtime on D1-21	Cycles 1-n
Elotuzumab	20 mg/kg ^b	IV	D1 of each cycle	Cycles 1-n
^a LTD=last tolerated dose ^b If a subject's weight changes by more than 10% from cycle 1 day 1 of induction the dose of elotuzumab should be recalculated. This re-calculated weight should be used as the new baseline weight.				

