10.2.5 Adverse Events Associated with Carfilzomib

For complete information on safety, please refer to the latest version of the prescribing information for carfilzomib, which can be found at www.kyprolis.com.

The safety of carfilzomib in combination with lenalidomide and dexamethasone (KRd) was evaluated in an open-label randomized study in patients with relapsed multiple myeloma. Adverse Reactions that occurred at a rate of $\geq 10\%$ in the KRd arm (n=392) during the first 12 cycles of therapy are in the table below.

Adverse Reaction	KRd Arm n (%)	
	Any Grade	\geq Grade 3
Anemia	138 (35)	53 (14)
Asthenia	54 (14)	11 (3)

Back Pain	41 (11)	4 (1)
Bronchitis	55 (14)	5 (1)
Constipation	68 (17)	0
Cough	93 (24)	2 (1)
Diarrhea	119 (30)	8 (2)
Dyspnea	71 (18)	8 (2)
Fatigue	113 (29)	23 (6)
Hyperglycemia	43 (11)	18 (5)
Hypertension	41 (11)	12 (3)
Hypocalcemia	55 (14)	10 (3)
Hypokalemia	78 (20)	22 (6)
Insomnia	64 (16)	6 (2)
Muscle spasms	92 (24)	3 (1)
Nausea	63 (16)	1 (0)
Neutropenia	124 (32)	104 (27)
Peripheral edema	59 (15)	3 (1)
Peripheral neuropathies	43 (11)	7 (2)
Pneumonia	54 (14)	35 (9)
Pyrexia	93 (24)	5 (1)
Rash	45 (12)	5 (1)
Thrombocytopenia	100 (26)	58 (15)
Upper Respiratory Tract Infection	87 (22)	7 (2)
Venous Embolic and Thrombotic Events	49 (13)	16 (4)
Viral upper respiratory tract infection	55 (14)	0

Laboratory abnormalities \geq Grade 3 reported at a rate of $\geq 10\%$ in the KRd arm included decreases in the following (% of patients): lymphocytes (46%), ANC (39%), phosphorus (31%), platelets (26%), total WBC (25%), hemoglobin (15%) and potassium (11%). Increased glucose (14%) was also reported.

The following warnings are associated with the use of carfilzomib (from the August 2020 prescribing information):

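### The planned safety summary pools 16 weeks of four-drug induction with open-ended two-drug maintenance, so the toxicity of KRd+elotuzumab induction cannot be read from it

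*Combined protocol and SAP*

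**What the plan says.** Section 14.5.6 (Safety Analysis) states that "Incident rates for treatment-emergent adverse events, adverse events leading to study drug discontinuation, SAEs and deaths while on study therapy will be summarized". The first limb of its treatment-emergent definition is "An adverse event that occurs after treatment start that was not present at the time of treatment start"; the second covers worsening after treatment start. Neither limb has an end or a phase boundary. For exposure, the same section says "Cumulative dose and relative dose intensity will then be summarized for the study arm".

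Section 14.4 gives one safety population: "Analyses of other efficacy and safety endpoints will be conducted on the population of subjects who initiate treatment with elotuzumab". Sections 2.3 and 14.3.8 list the safety endpoints without a split or a fixed window.

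Section 5 describes "induction therapy comprised of 4 cycles of carfilzomib, lenalidomide, dexamethasone and elotuzumab", and then "Maintenance therapy comprised of elotuzumab and lenalidomide (R+elotuzumab) will start directly after induction and continue until relapse or progression". Section 5.2 fixes the join: "The first cycle of maintenance therapy will begin 4 weeks (28D) after the start of cycle 4 of induction". Carfilzomib appears only in Table 1 (induction). In maintenance, dexamethasone is elotuzumab premedication and not part of the regimen (Section 7, footnote 17).

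Section 12.3.1 collects AEs from Day 1 to 90 days after the last dose (less if new therapy starts), with start and stop dates. Section 14.5.1 sets primary, updated and final analyses but does not say which of them include safety.

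**The concern.** The untested element is elotuzumab added to a carfilzomib-containing triplet. Section 1.4 supports its safety from elotuzumab with bortezomib. The induction toxicity of the quadruplet is therefore a main output of the trial, and the planned summary does not deliver it. A first event in the second week of induction and a first event in the second year of maintenance enter the same count. A subject who has an event in induction adds nothing to a subject-level count when the same event recurs in maintenance.

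The protocol itself expects the phases to differ. Section 1.4 says dexamethasone is dropped after induction to reduce long-term toxicity, and a pooled summary cannot show whether that happened. The KRd figures quoted in Section 10.2.5 have a stated window: "Adverse Reactions that occurred at a rate of $\geq 10\%$ in the KRd arm (n=392) during the first 12 cycles of therapy". A pooled, open-ended figure has none, and a crude proportion would depend on how long subjects stay on maintenance, which itself depends on efficacy.

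Exposure has the same problem. Elotuzumab and lenalidomide doses and schedules differ between Tables 1 and 2, yet one relative dose intensity per drug is planned over both phases.

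**Working it through.** The safety section states no figure to reproduce, so this is an illustration under stated assumptions.

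**Inputs from the documents**
- Induction: 4 × 28 = 112 days = 16 weeks; 112/30.4375 = 3.68 months (Sections 5, 5.2).
- Accrual: 24 months, taken as uniform (Section 5).
- Median PFS with KRd: 15.4 and 26.3 months (Section 1.2), used as the range for median time on treatment.

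**Assumptions**
- Time on treatment is exponential: h = ln 2/15.4 = 0.0450 or ln 2/26.3 = 0.0264 per month.
- The event has a 10% risk over a completed induction: λ = −ln(0.9)/3.68 = 0.0286 per month.
- The maintenance hazard is rλ, with r = 0.5 as the main case.
- Cuts fall F = 3.68, 36 and 60 months after the last subject starts. Follow-up c is then uniform from F to F + 24. Events after treatment stops are ignored.

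**Crude proportion with at least one event**
- Induction part: λ/(λ+h) × (1 − S), where S = exp[−(λ+h) × 3.68].
- Maintenance part: S × rλ/k × (1 − A), where k = rλ + h and A is the mean of exp[−k(c − 3.68)] over c.

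Median 15.4, r = 0.5: S = 0.763 and k = 0.0593.
- Induction part: 0.389 × 0.237 = 0.092.
- Primary cut: A = 0.533; maintenance part 0.763 × 0.241 × 0.467 = 0.086; total **17.8%**.
- 3-year cut: A = 0.078; maintenance part 0.170; total **26.2%**.

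Median 26.3, r = 0.5: S = 0.817 and k = 0.0407.
- Induction part: 0.521 × 0.183 = 0.095.
- Primary cut: A = 0.638; maintenance part 0.104; total **19.9%**.
- 3-year cut: A = 0.172; maintenance part 0.238; total **33.3%**.

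A simulation of 400,000 subjects agrees with these totals. Across r (each range runs over the two medians):

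| Maintenance/induction hazard r | Primary cut | 3 years | 5 years |
|---|---|---|---|
| 0 | 9.2–9.5% | 9.2–9.5% | 9.2–9.5% |
| 0.25 | 14–15% | 19–23% | 19–25% |
| 0.5 | 18–20% | 26–33% | 27–36% |
| 1 | 25–28% | 38–48% | 39–51% |

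The r = 0 row is just below 10% because some subjects stop during induction.

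**Person-time rate**

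With w the induction share of on-treatment time, the rate per patient-year is 12λ[w + r(1 − w)]. The share w is 28–32% at the primary cut, 13–17% at 3 years and 11–16% at 5 years. For r = 0.5 and median 15.4:
- primary cut: 0.344 × (0.317 + 0.5 × 0.683) = 0.226
- 3 years: 0.344 × (0.174 + 0.5 × 0.826) = 0.202

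For median 26.3 the rate goes from 0.220 to 0.194. The same data thus give a crude proportion that rises and a person-time rate that falls. Which one would be reported is not stated.

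**The case against.** The other side has several good points.

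- **Section 14.5.6 does not forbid tables by phase.** True, but it does not plan them. Its definition and Section 14.4 describe one population and one open-ended window. In an open-label trial, the window and denominator would then be chosen with the results in view.
- **The reference to the study arm applies only to dose summaries.** Correct. The pooling of AEs follows from the treatment-emergent definition and the population, not from that phrase.
- **A reader might infer that the reported rates rise at every data cut.** The documents do not support this. Section 14.5.1 never says that safety is repeated, a crude proportion is flat for events confined to induction, and a person-time rate can fall.
- **A reader might infer that carfilzomib-related harms cannot be separated from late maintenance events at all.** That is also too strong. AE dates and attribution are recorded, and carfilzomib exposure is induction-only. The planned summary lacks the separation; the data do not.
- **The illustration may be too large.** Median PFS comes from trials with other carfilzomib schedules and ignores stopping for toxicity, so it may overstate time on drug. Some toxicity is front-loaded: Section 1.3.4.1 reports 70% of infusion reactions in the first cycle. For such events r is near 0 and pooling changes little.
- **The safety objective in Section 2.3 is not limited to induction, and a 16-week table would not match the 12-cycle KRd window either.** Both are true. The overall summary should therefore stay, and nothing here requires induction to be ranked as the primary safety result.

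**Conclusion.** The point holds as a gap in the analysis plan, worth closing before the safety tables are produced. As written, Section 14.5.6 gives no readable toxicity figure for the 16-week KRd+elotuzumab induction. For an event with a 10% induction risk that continues at half the hazard in maintenance, a pooled crude proportion would be about 18–20% at the primary cut and 26–33% at 3 years. The distortion is already present at the primary analysis, because early enrollees are well into maintenance by then.

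These figures rest on exponential treatment time with median 15.4 to 26.3 months, uniform 24-month accrual and the assumed hazard ratio. They range from no distortion (r = 0) to 38–48% at 3 years (r = 1). The updated analysis may also come before 3 years if PFS censoring reaches 20% first.

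The VGPR+ test is unaffected.

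**What to change.** In Section 14.5.6 keep the overall summary and add separate tables of TEAEs, grade 3 or higher TEAEs, AEs leading to discontinuation, SAEs and deaths for:

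- **Induction:** first dose to the day before maintenance C1D1. For subjects who do not start maintenance, use a fixed stated window, for example through day 112, and list later events up to the end of AE reporting separately. The denominator is all treated subjects. The fixed window matters: running it to the end of AE reporting would give subjects who stop early up to 90 extra days after their last dose.
- **Maintenance:** events new or worsened relative to maintenance C1D1. The denominator is subjects who start maintenance.

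Also:

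- define incident rate as the proportion of subjects with at least one event, and add rates per subject-time for maintenance and overall;
- split cumulative dose and relative dose intensity by phase for elotuzumab and lenalidomide (carfilzomib is already induction-only);
- state in Section 14.5.1 which analyses include safety.

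The cost is SAP wording, a phase flag derived from AE and dosing dates, more tables and smaller counts in each. No new data and no change to treatment are needed.
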